How old were you when you **first** smoked a cigarette?

Enter INTEGER

OR

-1 Do not know

OR

-3 Prefer not to answer

If you do not remember when you had your first cigarette, please enter your best guess.

[V2 (NHS3)]

How old were you when you first used an e-cigarette (vaping)?

Enter INTEGER

OR

-1 Do not know

OR

-3 Prefer not to answer

[V3 (NHS3)]

When you used your first e-cigarette (vaping)

SELECT one of 6 from

- 1 I had never smoked tobacco cigarettes
- 2 I was a current smoker of tobacco cigarettes and had no plans to quit
- 3 I was a current smoker of tobacco cigarettes and was planning to quit
- 4 I was a current smoker of tobacco cigarettes and was planning to reduce smoking
- 5 I had stopped smoking tobacco cigarettes
- 3 Prefer not to answer

[TOBACCO_B (CONNECT)]

Have you ever regularly used any of these **tobacco** products?

Select all that apply.

TOGGLE of 8 choices

[Require ≥1 choices]

- 0 Cigarettes (manufactured or hand-rolled)
- 1 Electronic delivery devices that can be vaped, such as e-cigarettes (e.g., UWELL, Vype, Vuse, Vapouriz, WizMix). → **GO TO V2**
- 2 Cigars, cigarillos, or little filtered cigar (e.g., Montecristo, Romeo Y Julieta, Cohiba, Davidoff, Neos red) → **GO TO S11**
- 3 Chewing tobacco, snus, snuff, **Gutkha**, or dip (e.g., Skruf, Tulsi, Sikandar, conwood, Al Capone powder) → **GO TO S11**
- 4 Shisha, hookah or water pipe → **GO TO S11**
- 5 Tobacco pipe → **GO TO S11**
- 6 I have **not** used any of these tobacco products **[EXCLUSIVE]** → **GO TO S11**
- 3 Prefer not to answer **[EXCLUSIVE]** → **GO TO S11**

We understand that the meaning of "regular basis" might be different for different people. When you answer this question, please think about what "regular basis" means to you.

[S3B (UKB/CONNECT)]

How old were you when you first started smoking **on a regular basis**?

Enter INTEGER

OR

-1 Do not know

OR

-3 Prefer not to answer

We understand that the meaning of "regular basis" might be different for different people. When you answer this question, please think about what "regular basis" means to you.

If you don't know, please give us your best estimate

[S2AA (CONNECT)]

On how many occasions have you smoked cigarettes in your life?

SELECT one of 5 from

- 0 10 or less → **GO TO S11**
- 1 11—49 → **GO TO S11**
- 2 50—99
- 3 100 or more
- 3 Prefer not to answer → **GO TO S11**

[S4(UKB/CONNECT)]

What type of cigarettes have you mainly smoked?

SELECT one of 6 from

- 1 Manufactured cigarette
- 2 Hand-rolled cigarettes
- 7 None of the above
- 3 Prefer not to answer

If you smoke both hand-rolled, and manufactured cigarettes select the one that you smoke more of.

If you still currently smoke, report the type you smoke most frequently

[S1 (UKB/CONNECT)]

Do you smoke cigarettes now?

SELECT one of 4 from

- 1 Yes, every day
- 2 **Yes, some days**
- 3 **Yes, but rarely**

- 0 No, not at all -> S2 (UKB)
- 3 Prefer not to answer -> S2 (UKB)

[S1A (CONNECT)]

On the days that you smoke, how many cigarettes do you smoke **per day on average**?
Please provide the number of cigarettes, not the number of packs.

Enter INTEGER

OR

-10 Less than one a day

OR

-1 Do not know

→ GO TO S5A

Count the total number of cigarettes (including both hand-rolled and manufactured cigarettes)

For hand-rolled cigarettes:

- One ounce of tobacco makes about 30 cigarettes.
- One gram of tobacco makes about 1 cigarette.

[S2 (UKB/CONNECT)]

In the past, how often have you smoked cigarettes?

SELECT one of 4 from

- 1 Smoked every day -> S2B
- 2 Smoked some days
- 3 Smoked rarely
- 3 Prefer not to answer

[S4AA (UKB/CONNECT)]

Did you ever smoke cigarettes on **most or all days**?

SELECT one of 3 from

- 0 No → GO TO S5A
- 1 Yes
- 3 Prefer not to answer → GO TO S5A

[S4AB (CONNECT)]

On the days that you smoked how many cigarettes did you smoke **per day on average**?
Please provide the number of cigarettes, not the number of packs.

Enter INTEGER

OR

-10 Less than one a day

OR

-1 Do not know

Count the total number of cigarettes (including both hand-rolled and manufactured cigarettes if both are smoked)

For hand-rolled cigarettes:

- One ounce of tobacco makes about 30 cigarettes.
- ONE GRAM OF TOBACCO MAKES ABOUT 1 CIGARETTE.

[S8 (UKB)]

How old were you when you last smoked cigarettes on most days? S11

Enter INTEGER

OR

-1 Do not know

OR

-3 Prefer not to answer

[S5A (UKB)]

Compared to 10 years ago do you smoke...

SELECT one of 4 from

- 1 More nowadays? -> **GO TO S9**
- 2 About the same? -> **GO TO S9**
- 3 Less nowadays? -> **GO TO S5B (UKB)**
- 3 Prefer not to answer -> **GO TO S9**

[S5B (UKB)]

SHOW IF (S5A = 3) OR (S1 > S1A AND S1 != 0 AND S1 != -3)

Why did you reduce your smoking?

(You can select more than one answer)

TOGGLE of 19 choices

[Require ≥1 choices]

- 1 Advice from a GP/Health professional
- 2 TV advert for a nicotine replacement product
- 3 Government TV/radio/Press advert
- 4 Hearing about a new stop smoking treatment
- 5 A decision that smoking was too expensive
- 6 Being faced with smoking restrictions
- 7 I knew someone else who was stopping
- 8 Seeing a health warning on a cigarette pack
- 9 Being contacted by my local NHS Stop Smoking Services
- 10 Health problems I had at the time
- 11 A concern about future health problems
- 12 Attending a local stop smoking activity or event
- 13 Something said by family/friends/children
- 14 A significant birthday
- 15 The coronavirus outbreak
- 16 Restrictions on where I could smoke

- 7 None of the above [**EXCLUSIVE**]
- 1 Do not know [**EXCLUSIVE**]
- 3 Prefer not to answer [**EXCLUSIVE**]

→ GO TO S9

[S9 (UKB)]

In the time that you smoked, did you ever stop for more than 6 months?

SELECT one of 4 from

- 1 Yes -> **GO TO S10**
- 0 No -> **IF (S1 == 0 AND S3 != -3) GO TO S10 ELSE GO TO S11**
- 1 Do not know -> **IF (S1 == 0 AND S3 != -3) GO TO S10 ELSE GO TO S11**
- 3 Prefer not to answer -> **IF (S1 == 0 AND S3 != -3) GO TO S10 ELSE GO TO S11**

[S10 (TOOLKIT)]

Why did you stop smoking?
(You can select more than one answer)

TOGGLE of 19 choices

[Require ≥1 choices]

- 1 Advice from a GP/Health professional
- 1 TV advert for a nicotine replacement product
- 1 Government TV/radio/Press advert
- 1 Hearing about a new stop smoking treatment
- 5 A decision that smoking was too expensive
- 6 Being faced with smoking restrictions
- 7 I knew someone else who was stopping
- 8 Seeing a health warning on a cigarette pack
- 9 Being contacted by my local NHS Stop Smoking Services
- 10 Health problems I had at the time
- 11 A concern about future health problems
- 12 Attending a local stop smoking activity or event
- 13 Something said by family/friends/children
- 14 A significant birthday
- 15 The coronavirus outbreak
- 16 Restrictions on where I could smoke

- 7 None of the above **[EXCLUSIVE]**
- 1 Do not know **[EXCLUSIVE]**
- 3 Prefer not to answer **[EXCLUSIVE]**

[V4 (NHS3)]

How often, on average, did you use e-cigarettes (vaping) during the past 12 months?

SELECT one from 12

- 1 Never
- 2 Less than 1 time/mo
- 3 2-3 times/mo
- 4 1-2 times /week
- 5 3-6 times /week
- 6 1-4 times /day
- 7 5-14 times /day
- 8 15-24 times /day
- 9 25– 34 times /day
- 10 35 – 44 times /day
- 11 More than 45 times /day
- 3 Prefer not to answer

[V5 (NHS3)]

What type of e-liquids/cartridges do you or did you use in your e-cigarettes?

CHOOSE ALL THAT APPLY

- 1 Fruit/dessert flavour WITHOUT nicotine
- 2 Fruit/dessert flavour WITH nicotine
- 3 Menthol flavour WITHOUT nicotine
- 4 Menthol flavour WITH nicotine
- 5 Tobacco flavour WITHOUT nicotine
- 6 Tobacco flavour WITH nicotine
- 7 Marijuana or THC concentrate
- 8 Alcohol
- 9 Other:
- 3 Prefer not to answer

[S11V2 (CONNECT)]

In **the past year**, about how often were you around tobacco smoke from other people smoking in your home or at work?

SELECT one of 8 from

- 1 Every day
- 1 Most days of the week
- 2 A few days per week
- 3 One day per
- 4 A few days per month
- 5 One day per month
- 6 A few days per
- 0 Never → **GO TO A1**
- 3 Prefer not to answer → **GO TO A1**

[S12 (UKB)]

On days you were around other people's tobacco smoke in **the past year** in your home or work, about how many hours per day were you around it?

SELECT one of 6 from

- 0 Less than 1 hour per day
- 1 1 to 2 hours per day
- 2 3 to 5 hours per day
- 3 6 to 9 hours per day
- 4 10 to 15 hours per day
- 5 More than 15 hours per day
- 3 Prefer not to answer

IF TOBACCO _B = 1 GO TO V2 ELSE GO TO A1

[A1 (UKB)]

About how often do you drink alcohol?

SELECT one of 7 from

- 1 Daily or almost daily
- 2 Three or four times a week
- 3 Once or twice a week
- 4 One to three times a month -> GO TO A2B (UKB)
- 5 Special occasions only -> GO TO A2B (UKB)
- 6 Never -> GO TO A1A (UKB)
- 3 Prefer not to answer -> GO TO END SECTION 3

If this varies a lot, please provide an average considering your intake over the last year

[A1A (UKB)]

Did you previously drink alcohol?

SELECT one of 3 from

- 1 Yes -> GO TO A7A (UKB)
- 0 No -> GO TO END SECTION 3
- 3 Prefer not to answer -> GO TO END SECTION 3

[A2B (UKB)]

In an average MONTH, how many glasses of RED wine would you drink?
(There are six glasses in an average bottle)

Enter INTEGER

OR

- 1 Do not know

OR

- 3 Prefer not to answer

Please include sparkling red wine here.

[A2C (UKB)]

In an average MONTH, how many glasses of WHITE wine or champagne would you drink?
(There are six glasses in an average bottle)

Enter INTEGER

OR

-1 Do not know

OR

-3 Prefer not to answer

Please include sparkling white wine, prosecco and rosé here.

[A2E (UKB)]

In an average MONTH, how many pints of beer or cider would you drink?
(Include bitter, lager, stout, ale, Guinness)

Enter INTEGER

OR

-1 Do not know

OR

-3 Prefer not to answer

[A2A (UKB)]

In an average MONTH, how many measures of spirits or liqueurs would you drink?
(there are 25 standard measures in a normal sized bottle; spirits include drinks such as whisky, gin, rum, vodka, brandy)

Enter INTEGER

OR

-1 Do not know

OR

-3 Prefer not to answer

[A2F (UKB)]

In an average MONTH, how many glasses of fortified wine would you drink? (There are 12 glasses in an average bottle) (Fortified wines include drinks such as sherry, port, vermouth)

Enter INTEGER

OR

-1 Do not know

OR

-3 Prefer not to answer

Fortified wines include: Sherry, Port, Vermouth, Muscat, Madeira, Malaga, Tokay, Frontignan, Frontignac.

[A2G (UKB)]

In an average MONTH, how many glasses
of other alcoholic drinks (such as alcopops) would you drink?

Enter INTEGER

OR

-1 Do not know

OR

-3 Prefer not to answer

[A3B (UKB)]

In an average WEEK, how many glasses of RED wine would you drink?
(There are six glasses in an average bottle)

Enter INTEGER

OR

-1 Do not know

OR

-3 Prefer not to answer

Please include sparkling red wine here.

[A3C (UKB)]

In an average WEEK, how many glasses of WHITE wine or champagne would you drink?
(There are six glasses in an average bottle)

Enter INTEGER

OR

-1 Do not know

OR

-3 Prefer not to answer

Please include sparkling white wine, prosecco and rosé here.

[A3E (UKB)]

In an average WEEK, how many pints of beer or cider would you drink?
(Include bitter, lager, stout, ale, Guinness)

Enter INTEGER

OR

-1 Do not know

OR

-3 Prefer not to answer

[A3A (UKB)]

In an average WEEK, how many measures of spirits or liqueurs would you drink?

(there are 25 standard measures in a normal sized bottle; spirits include drinks such as whisky, gin, rum, vodka, brandy)

Enter INTEGER

OR

-1 Do not know

OR

-3 Prefer not to answer

For mixed drinks that contain spirits or liqueurs, count one bottle as one measure. There is a question later on alcopops

[A3F (UKB)]

In an average WEEK, how many glasses of fortified wine would you drink?
(There are 12 glasses in an average bottle; Fortified wines include drinks such as sherry, port, vermouth)

Enter INTEGER

OR

-1 Do not know

OR

-3 Prefer not to answer

Fortified wines include: Sherry, Port, Vermouth, Muscat, Madeira, Malaga, Tokay, Frontignan, Frontignac.

[A3G (UKB)]

In an average WEEK, how many glasses of other alcoholic drinks (such as alcopops) would you drink?

Enter INTEGER

OR

-1 Do not know

OR

-3 Prefer not to answer

[A5 (UKB)]

When you drink alcohol is it usually with meals?

SELECT one of 5 from

1 Yes

0 No

-6 It varies

-1 Do not know

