2.5. Physical measurements

We will assess physical measurements when participants provide blood samples for those metrics and in locations where this is feasible and cost-effective. Although height and weight are typically accurately self-reported within a population⁴⁴, in-person assessment of these metrics provides individual accuracy which is important for a variety of disease risk estimations as well as participant feedback that incorporates such information⁴⁵. Weight is associated with many diseases including cardiovascular disease and cancer. Height can be used to calculate body mass index (BMI) from weight which has greater predictive accuracy for disease, and height also an independent predictor of certain cancers, vascular disease and all-cause mortality.

Capturing height and weight in-person can easily be extended to measurement of other physical characteristics such as waist circumference⁴⁶, bioimpedance⁴⁷, and blood pressure. Waist circumference is highly correlated with intra-abdominal fat mass while bioimpedance analysis is a non-invasive, low-cost analysis of body composition. Waist circumference and bioimpedance analysis have each been shown to be associated with a higher risk of diabetes and vascular events independently of BMI. Excessive intra-abdominal fat may be more harmful to health than fat elsewhere due to higher release of free fatty acids into the portal bloodstream which lowers the body's sensitivity to insulin, and alters the balance of blood lipids.

⁴⁴ Celis-Morales et al (*Genes Nutr*, 2015) How reliable is internet-based self-reported identity, socio-demographic and obesity measures in European adults? <https://pubmed.ncbi.nlm.nih.gov/26143178/>

⁴⁵ Newell et al (*Am J Prev Med*, 2017) The accuracy of self-reported health behaviors and risk factors relating to cancer and cardiovascular disease in the general population 1: A critical review. <https://pubmed.ncbi.nlm.nih.gov/10987638/>

⁴⁶ Ross et al (*Nat Rev Endocrinol*, 2020) Waist circumference as a vital sign in clinical practice: a Consensus Statement from the IAS and ICCR Working Group on Visceral Obesity. <https://pubmed.ncbi.nlm.nih.gov/32020062/>

⁴⁷ Böhm et al (*Eur J Clin Nutr*, 2017) The use of bioelectrical impedance analysis for body composition in epidemiological studies. <https://pubmed.ncbi.nlm.nih.gov/23299875/>

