3.8. Phlebotomy and physical measurements

We will record physical measurements and collect a blood sample from each consented participant at an in-person appointment in one of the following settings:

1. Community covering pharmacies, mobile units, and 'pop-up' clinics
2. Existing NHSBT appointments for blood donations
3. Existing NHS appointments for health care phlebotomy

Participants will have a choice in where they donate their blood and undergo a brief physical assessment. Location choice will largely be within the community route (pharmacy collaborations, Our Future Health mobile units and 'pop-up' clinics). If the participant has been recruited through an NHS route, then they will likely automatically be in an existing phlebotomy route such as blood donation, or primary or secondary health care.

As general practice, two vials of blood will be drawn from participants. However, up to five vials of blood could be taken for purposes such as quality control or where samples may be unusable. Blood samples will be used to extract DNA and conduct genotyping, as well as conduct baseline assessments of cholesterol and HbA1c and will be sent to our biobank for long-term storage. At all opportunities the blood collection time and date, and time of last significant meal will be collected at the time of blood draw. Physical measurements will also be taken at this time including blood pressure, height, weight, and waist circumference.

Point of care testing (POCT) for cholesterol will also be offered to participants at their clinic appointment. The cholesterol test will be performed using a finger-prick blood test with the Mission POCT device, which is approved for use by the NHS. Whilst all participants will have the

option of receiving the results of their POCT on a proforma, alongside other physical measurements taken at the appointment, these measurements are taken for research purposes only –not clinical or diagnostic purposes and are not a personal health check/substitute for the NHS Health Check.

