Select the option that best describes your current gender identity

SELECT 1 from

- 1 Gender-fluid
- 2 Man
- 3 Nonbinary
- 4 Woman
- 5 I don't identify with any option provided
- 3 Prefer not to answer

[GENDER_B (OXFORD_EDI)]

Do you identify as trans or do you have a trans history?

SELECT 1 from

- 1 Yes
- 2 No
- 3 Prefer not to answer

[SEXUAL_ORIENTATION (CENSUS 2021)]

Which of the following best describes your sexual orientation?

SELECT 1 from

- 1 Asexual
- 2 Bisexual
- 3 Gay
- 4 Heterosexual/Straight
- 5 Lesbian
- 6 Pansexual
- 7 Queer
- 8 Other sexual orientation not listed
- 3 Prefer not to answer

This question is voluntary, so you can respond "prefer not to answer" if you prefer

"Straight/Heterosexual" means that you're only attracted to people of the opposite sex

"Gay or Lesbian" means that you're attracted to people of the same sex

"Bisexual" means that you're attracted to more than one sex

"Pansexual" means that you're attracted to people regardless of their sex or gender identity

"Asexual" means that you're not attracted to any sex

We realise we have not listed every sexual orientation. If your sexual orientation is not described by any of these categories, please select the "other sexual orientation not listed" option.

[HEIGHT_M (STRIDES)]

We are now going to ask you to tell us how tall you are.
How would you prefer to enter your height?

SELECT 1 from

- 1 Feet/inches -> **GO TO HT_FT**
- 2 Metres/centimetres -> **GO TO HT_CM**
3. I do not want to report my height -> **GO TO WEIGHT_M**

[HT_FT]

What is your height (Without shoes)?
If you don't know, please provide a best guess

Enter INTEGER

[Require]:

3ft0– 7ft 11 as given

OR

-3 Prefer not to answer

[HT_CM]

What is your height (Without shoes)?
If you don't know, please provide a best guess

Enter INTEGER

[Require]:

90cm - 2m 99cm as given]

OR

-3 Prefer not to answer

[WEIGHT_M (STRIDES)]

We are now going to ask you to tell us how much you weigh.
How would you prefer to enter your weight?

SELECT 1 from

- 1 Stones/pounds -> **GO TO WT_ST**
- 2 Kilograms -> **GO TO WT_CM**
- 3 I do not want to report my weight -> GO TO Language

[WT_ST (STRIDES)]

What is your weight (Without shoes/heavy clothing)?
If you don't know, please provide a best guess

Enter INTEGER

[Require min value

3 stones

max value

63 stones

OR

-3 Prefer not to answer

[WT_KG (STRIDES)]

What is your weight (Without shoes/heavy clothing)?
If you don't know, please provide a best guess

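### Appendix E sends self-reported weight in kilograms to an item that is not defined, and gives the stones/pounds item neither a pounds entry nor an exit

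*Protocol*

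**What the plan says.** Appendix E, Section 1, asks for weight in three items.

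- WEIGHT_M asks which unit the participant prefers. Its two unit options are routed "Stones/pounds -> GO TO WT_ST" and "Kilograms -> GO TO WT_CM".
- WT_ST takes one integer, with a minimum of 3 stones and a maximum of 63 stones. No pounds part is written and no onward route is given.
- WT_KG follows directly, takes one integer from 20 to 400 kg, and is followed by LANGUAGE.

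The matching height item, HT_FT, is also specified as an integer entry, but its limits are "3ft0– 7ft 11 as given", that is, in both feet and inches. It too has no written exit, and HT_CM comes next.

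The main text gives a second source of weight. Section 3.8 says "We will record physical measurements and collect a blood sample from each consented participant at an in-person appointment", and "Physical measurements will also be taken at this time including blood pressure, height, weight, and waist circumference". Section 2.5 is more guarded: measurement takes place "in locations where this is feasible and cost-effective".

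**The concern.** Appendix E is the instrument to be built, and Section 3.6 says that it includes the changes made after piloting. Its routing and entry formats therefore determine what is stored. One unit option leads to a label with no item behind it. The other leads to an item that cannot hold what the option offers.

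Section 2.4 gives body weight as an example of what questionnaires are meant to supply, and Section 2.5 ties weight and BMI to disease-risk estimation. Section 2.5 also remarks "Although height and weight are typically accurately self-reported within a population". That remark can only carry over to this cohort if the questionnaire records the reported value at adequate precision. At stake is self-reported weight that is missing in one unit group and coarser in the other, wherever it is the only weight available.

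**Working it through.** The protocol states no figure on this point, so there is none to reproduce. The check has two parts.

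**Routing, set side by side**

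| Choice in WEIGHT_M | Target printed | Target defined? | Next item as printed |
|---|---|---|---|
| Stones/pounds | WT_ST | Yes; integer, 3 to 63 stones | WT_KG (no exit written) |
| Kilograms | WT_CM | No | Undefined |

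WT_KG is complete in itself, but it is reached only by running on from WT_ST.

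The stone limits convert to 3 × 6.350 = 19.05 kg and 63 × 6.350 = 400.07 kg. They match the 20 to 400 kg limits of WT_KG, so they are range checks on the same scale. They do not by themselves state a resolution.

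**Size of a whole-stone entry**

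Inputs: 1 stone = 14 lb = 6.350 kg (unit conversion). Heights, weight SDs and BMI distributions are assumptions, because the protocol gives none.

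1. Rounded to the nearest stone: the largest error is 7 lb = 3.18 kg. Divided by 1.70² = 2.89, this is 1.10 kg/m2. For heights of 1.80 m to 1.50 m the range is 0.98 to 1.41 kg/m2.
2. Precision lost by rounding: the error variance is 6.350²/12 = 3.36 kg². The share of weight variance kept is SD²/(SD² + 3.36), which is 97.7% at an SD of 12 kg and 99.0% at 18 kg.
3. Effect at BMI 30 under rounding, by simulation with mean height 1.69 m (SD 0.095) and BMI mean 27 (SD 4.5) or 27.5 (SD 5.5): bias about 0, with 4.0% and 3.7% misclassified.
4. If pounds are dropped instead: the largest error is 13 lb = 5.90 kg, or 5.90/2.89 = 2.04 kg/m2. The mean error is 6.5 lb = 2.95 kg, or 1.02 kg/m2, always downward. In the same simulation the share at BMI 30 or above falls from 25.2% to 18.7%, or from 32.5% to 26.1%.
5. Comparator, whole kilograms: the largest error is 0.5/2.89 = 0.17 kg/m2 (0.15 to 0.22 over the same heights), with about 0.6% misclassified at BMI 30.
6. With a pounds field: the step falls from 6.35 kg to 0.45 kg, so the largest error is 0.23/2.89 = 0.08 kg/m2.

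**The case against.** The strongest reply is that both faults are slips of drafting with little consequence. Much of it stands.

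- *The intended kilogram target is plain.* Two units are offered, two weight items follow, and WT_CM looks like a carry-over from HT_CM just above. Similar label slips occur elsewhere in Appendix E, such as HEART_MD_B for HEART_MED_B. Kilogram data are lost only if a builder follows the printed label literally.
- *Whole-stone entry is an inference.* HT_FT is also marked as an integer yet covers feet and inches, so the integer instruction alone does not exclude a two-part entry. What remains is that HT_FT writes both units into its limits and WT_ST does not.
- *Read strictly, stones users run on into WT_KG* and would be asked their weight again in kilograms. So coarsening arises if the missing exit is supplied in the build and the missing pounds field is not. This shows that the exit needs fixing too; it does not make the item sound.
- *Dropping pounds is not the expected behaviour.* The questionnaire's introduction tells participants to choose the nearest response when no exact one is available, which points to rounding.

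A reader might go further and infer that self-reported weight fails in both units, or that BMI is lost to the cohort. The documents do not support that: WT_KG is fully specified, and Section 3.8 plans measured height and weight for each consented participant. A reader might also suppose that unit choice follows age and so biases comparisons by age. The protocol contains nothing on unit preference.

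**Conclusion.** The point holds as a specification error of modest size. The kilogram route names an undefined item, and the stones/pounds item has no pounds entry and no exit. These are facts of the text.

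The consequences are conditional. If the route is built literally, self-reported weight is missing for kilogram users. If WT_ST stores whole stones and participants round, the error is at most 3.2 kg (1.1 kg/m2 at an assumed 1.70 m), with no mean bias and 1% to 2.3% of weight variance lost. The downward bias of about 1 kg/m2 requires that pounds be dropped, so it is an outer case and not the expected one.

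The effect falls mainly on participants without an in-person measurement. Their share is not stated. Section 3.8 promises measurement for everyone, whereas Section 2.5 limits it by location. The running text on blood donors (Section 3.8.2) and on routine hospital blood draws (Section 3.8.3) describes only a blood sample; Section 3.8.3 mentions physical measurements for hospital pop-up clinics. Self-report may therefore be the only weight on some routes, but the protocol does not settle this.

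**What to change.** In Appendix E, Section 1:

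- change the kilogram route in WEIGHT_M from WT_CM to WT_KG;
- give WT_ST two integer fields, stones (limits as now) and pounds (0 to 13);
- add an exit from WT_ST to LANGUAGE, so that stones users are not also asked for kilograms;
- check HT_FT in the same edit and add an exit to WEIGHT_M, so that it does not run on into HT_CM.

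Self-reported weight then has similar precision in either unit, and the answer to WEIGHT_M already records which unit was used. The cost is one corrected label, one added field with its limits, and two routes. The burden on participants is one short extra entry for those who choose stones and pounds. The change is cheap before the questionnaire is built; asking again for weight across a cohort of up to 5 million would not be.

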- 3 Someone of the opposite sex
- 4 Someone of the same sex
- 4 Other
- 3 Prefer not to answer

→ GO TO D4

[MARITAL_STATUS_D (CENSUS 2021)]

Who was your registered civil partnership to?

SELECT 1 from

- 5 Someone of the opposite sex
- 6 Someone of the same sex
- 5 Other
- 3 Prefer not to answer

→ GO TO D4

[D4 (UKB)]

What type of accommodation do you live in?

SELECT one of 7 from

- 1 A house or bungalow
- 2 A flat, maisonette or apartment
- 3 Mobile or temporary structure (i.e. caravan)
- 4 Sheltered accommodation **-> GO TO D5A**
- 5 Care home **-> GO TO D5A**
- 7 None of the above
- 3 Prefer not to answer

Please select:

-A house or bungalow for any whole, detached, semi-detached or terraced (including end-terrace) house or bungalow.

-A flat, maisonette, or apartment for any purpose-built block of flats or tenement, part of a converted or shared house (including bed-sits) or within a commercial building (for example in an office building, or hotel, or over a shop).

-If none of the options apply, select 'None of the above'.

[D5 (UKB)]

Do you own or rent the accommodation that you live in?

SELECT one of 8 from

- 1 Own outright (by you or someone in your household)
- 2 Own with a mortgage
- 3 Rent - from local authority, local council, housing association, student accommodation
- 4 Rent - from private landlord or letting agency
- 5 Pay part rent and part mortgage (shared ownership)
- 6 Live in accommodation rent free
- 7 None of the above

-3 Prefer not to answer

Please select:

- Own outright if you or someone in your household owns the accommodation that you live in.
- Own with mortgage if you or someone in your household has a mortgage on the accommodation that you live in.

[D5A (UKB)]

Do you have any of the following in your home? (You can select more than one answer)

TOGGLE of 6 choices

[Require >1 response]

- 1 A gas hob or gas cooker
- 2 A gas fire that you use regularly in wintertime
- 3 An open solid fuel fire that you use regularly in wintertime
- 7 None of the above **[EXCLUSIVE]**
- 1 Do not know **[EXCLUSIVE]**
- 3 Prefer not to answer **[EXCLUSIVE]**

Select the answer which best describes how your home is mainly heated. If you use more than one type of heating equally, you can choose multiple answers. Solid fuel refers to wood or coal. Regular use is when you use this for most days of the week in the winter time.

[D5A1 (UKB)]

How many years have you lived at your current address?

Enter INTEGER

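### Item D5A requires at least two selections, which rejects None, Do not know, Prefer not to answer and any single appliance, and its help text asks a different question from its stem

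*Protocol*

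**What the plan says.** In Protocol Appendix E, Section 1 (About you and your household), the stem of D5A reads "Do you have any of the following in your home? (You can select more than one answer". The item is a "TOGGLE of 6 choices". Three choices are substantive: "A gas hob or gas cooker", "A gas fire that you use regularly in wintertime" and "An open solid fuel fire that you use regularly in wintertime". The other three are None of the above, Do not know and Prefer not to answer, and each is marked exclusive.

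The entry rule is "Require >1 response".

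The help text begins "Select the answer which best describes how your home is mainly heated". Its second sentence allows several answers only where types of heating are used to the same extent. The remaining help text defines solid fuel and regular use.

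Comparable multi-select items nearby (D7A in Section 1; D9, D9E and D12 in Section 2) require at least one choice. The introduction to Appendix E tells participants that they may choose Prefer not to answer when they do not wish to answer a question.

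**The concern.** There are two separate faults in one item.

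First, an exclusive code is always a single selection, so it can never meet a rule that demands more than one. The same holds for a home with only one of the three appliances. If the rule were programmed as written, the unexposed group could not be entered, and participants could not decline this item as the introduction says they may.

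Second, the stem asks what is present in the home, and its first option is a cooking appliance. The help text asks for the main means of heating. A hob is not heating, and a secondary fire is not the main heating, so a respondent guided by the help could leave out either.

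D5A is put to every participant: the two D4 answers that jump ahead lead to D5A, and everyone else arrives through D5. Section 3.6 says that the baseline questionnaire is meant to capture factors that data linkage cannot readily supply.

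**Working it through.** The plan states no figure for this item, so there is nothing to reproduce. The check is a count of response patterns.

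**Inputs, all from D5A:** 3 substantive options that may be combined; 3 exclusive codes; minimum number of selections 2, since more than 1 means at least 2.

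**Legitimate response patterns**
- Non-empty combinations of the 3 appliances: 2³ − 1 = 7
- Exclusive codes, each alone: 3
- Total: 7 + 3 = 10

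**Accepted under the rule as written (at least 2 selections)**
- Pairs of appliances: C(3,2) = 3
- All three appliances: C(3,3) = 1
- Exclusive codes: 0
- Accepted: 3 + 1 + 0 = 4 of 10

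**Rejected:** 3 single-appliance answers + 3 exclusive codes = 6 of 10.

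**True exposure states of a home:** 2³ = 8. Those with at least two appliances number 3 + 1 = 4 and can be recorded. Those with none (1) or exactly one (3) number 1 + 3 = 4 and cannot.

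**With a minimum of one selection:** accepted patterns 7 + 3 = 10 of 10; recordable states 7 combinations + None = 8 of 8.

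**Share of homes.** These are counts of patterns, not of people. A home with two or more of the three appliances must have at least one of the two fires, so

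P(at least two appliances) ≤ P(regular gas fire or regular open solid-fuel fire in winter).

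More than half of homes would therefore be blocked if fewer than half regularly used such a fire. The documents give no prevalence for either fire or for gas hobs, so the share stays unquantified.

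**Stem against help text**

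| | Stem and options | Help text, first two sentences |
|---|---|---|
| What is asked | Which appliances are in the home | How the home is mainly heated |
| Gas hob or cooker | Listed as option 1 | Outside the question, not heating |
| Secondary fire in regular winter use | Counts | Left out unless used as much as the main heating |
| Several answers | Allowed without condition | Only for heating types used equally |

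Requiring at least one choice cures the first fault and leaves the second untouched.

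**The case against.** The strongest reply is that the rule is a one-character slip that no one would build. The key to Appendix E says that bracketed text is not shown to participants, so the rule is a programming note. The permissive stem and the three exclusive codes make the intended minimum plain. Other bracketed notes are also unworkable: FH8B sets current age as the lower limit for years since the last smear, and WEIGHT_M routes to a WT_CM item when the kilogram item is labelled WT_KG. Section 3.6 reports that 95% of pilot participants who started the questionnaire finished it, which sits badly with a universal early item that turned people away.

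Much of this stands. A slip for ≥ is the likeliest explanation, and enforcement is not shown. Two limits remain. The pilots used the initial questionnaire, Appendix E is the revised one, and the documents do not say whether D5A changed. Appendix E is also the text from which the form would be built. A reading error from the PDF cannot be excluded, but ≥ survives on neighbouring items.

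On the help text, the reply is that the visible stem and option list name the hob, so few would be misled. That limits the likely effect but does not remove the contradiction, because help text is shown to participants. High completion says nothing about misreporting.

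A reader might infer that most homes cannot answer truthfully, or that the resulting bias can never be undone. The documents support neither. The first needs prevalences that they do not give. The second is not shown: people who stop at the item leave visible missing data. Only a false tick or an omitted appliance would be hidden in the stored codes, and how often either would happen is unknown.

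**Conclusion.** Both contradictions are on the face of the item and should be corrected. If the rule is applied as written and exclusivity is enforced, 6 of 10 legitimate response patterns are rejected and 4 of 8 true exposure states cannot be recorded. That count needs no outside assumption. It does not translate into a number of homes or a size of bias. The help-text conflict is independent of the sign and remains even if programmers silently read it as ≥. Its effect is a risk of omission among those who follow the help, of unknown size.

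The weight is modest. This is one exposure item in a questionnaire that takes 35 minutes on average, and no aim or precision table in the Protocol depends on it.

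**What to change.** Make two edits to D5A in Appendix E.

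1. Change the rule to [Require ≥1 choices], as on D7A, D9, D9E and D12. Keep None, Do not know and Prefer not to answer as exclusive.
2. Replace the first two help sentences with: *Select every appliance you have at home, whether used for cooking or heating.* Keep the definitions of solid fuel and regular use.

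Both edits are needed, since neither cures the other fault. They add no participant burden. They are best made before the short questionnaire in Section 3.7 is assembled, because it draws on the existing items. The one small downside is that D5A is tagged UKB and Section 3.6 aims for close alignment with such cohorts, so new help wording may slightly affect comparability with the source questionnaire, whose wording cannot be checked here.
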